## 6.9. Anti-Drug Antibodies

Samples tested for ADAs will be reported as positive or negative based on a non-domain specific confirmatory assay. Samples that are positive, and are further tested, will be reported as positive or negative for the IL-17A binding domain, positive or negative for the albumin binding domain, and/or positive or negative as a neutralizing ADA. Any continuous values of concentration (titers) will be summarized using observed data.

Subjects will be summarized at each scheduled visit according to the confirmatory test, with number (%) positive. Positive samples on the confirmatory test, that are further tested, will be reported according to each specific binding domain, with number (%) positive for the IL-17A binding domain, number (%) positive for the albumin binding domain, and number (%) positive for either (one or both) binding domain. Samples that are further tested on a neutralizing antibody assay will be reported as number (%) positive for neutralizing activity, with percentage calculated using the number that were positive according to the screening

test as the denominator. In addition, incidence persistent ADA will be summarized for IL-17A and albumin binding domain. Persistent ADA is characterized as treatment-induced ADA detected at two or more sampling time points during the treatment irrespective of any negative samples in between (including follow-up period if any).

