8.7. Immunogenicity Assessments

- Antibodies to izokibep will be evaluated in serum samples collected from all subjects according to the SoA ([Section 1.3](#)). Additionally, serum samples should also be collected at the final visit from subjects who discontinued study drug or were withdrawn from the study. These samples will be tested by the sponsor or sponsor's designee.
- Instructions for the collection and handling of biological samples will be provided in the Laboratory Manual by the sponsor or designee.
- Samples testing positive for binding antibodies may be further characterized and may be tested for neutralizing antibodies.
- The detection and characterization of antibodies to izokibep will be performed using a validated assay method by or under the supervision of the sponsor.
- The immunogenicity serum samples will be retained while research on izokibep or interventions of this class or PsA continues but no longer than 20 years or another period as per local requirements.

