9.3.5. Safety Analyses

Safety data will include summaries of exposure, AEs, TEAEs, SAEs, and laboratory data. No inferential statistics (*p*-values) will be reported for safety data.

Exposure will include the number of doses administered (including complete and incomplete doses) and reasons for missed or incomplete doses. Exposure will be reported through the planned collection of the primary endpoint and for the entire study. For subjects assigned to receive placebo who later receive izokibep, exposure will further be summarized by placebo and izokibep. Compliance will be summarized by placebo and izokibep and by phase (placebo controlled and after crossing over to active).

Adverse events and SAEs reported before the first administration of the study drug will be listed. All summaries will include only treatment-emergent events. The number of subjects who report 1 or more AEs, the number who report 1 or more severe AEs, the number who report 1 or more SAEs, and the number who report 1 or more AEs that lead to discontinuation of study drug will be summarized by treatment group during the primary phase of the study and overall. Subjects assigned to receive placebo who later receive izokibep will additionally be summarized by phase (placebo-controlled and after crossing over to active).

Laboratory data including ADAs will be summarized by treatment group and overall, at each planned collection timepoint.

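### SAP 6.9 takes the neutralizing-antibody percentage over positives on an undescribed screening test, while the section's ADA status, by-visit and binding-domain results rest on the confirmatory assay

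*SAP*

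**What the plan says.** SAP 6.9 sets ADA status in its opening sentence: "Samples tested for ADAs will be reported as positive or negative based on a non-domain specific confirmatory assay". It then says which samples are characterized further: "Samples that are positive, and are further tested, will be reported as positive or negative for the IL-17A binding domain". That sentence goes on to the albumin-binding domain and to neutralizing activity.

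Two summaries follow from this definition. By visit, "Subjects will be summarized at each scheduled visit according to the confirmatory test, with number (%) positive". For the binding domains, "Positive samples on the confirmatory test, that are further tested, will be reported according to each specific binding domain".

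The neutralizing summary comes next. It gives a number and a percentage positive, with the "percentage calculated using the number that were positive according to the screening" test as denominator. This is the only mention of a screening test in the section.

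The protocol does not supply another rule. Section 8.7 makes the neutralizing assay optional: "Samples testing positive for binding antibodies may be further characterized and may be tested for neutralizing antibodies". Section 9.3.5 says only "Laboratory data including ADAs will be summarized by treatment group and overall, at each planned collection timepoint" and gives no denominator. SAP 2.8 mentions binding-domain testing as possible further work and does not mention neutralization. SAP 4.5 defines the ADA Analysis Set but does not link it to this percentage.

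**The concern.** Within one section, the count that defines an ADA-positive result and the count that divides the neutralizing result come from different tests. Someone programming the sentence literally would need a screening-positive count that the section never asks for. The resulting percentage would also not sit on the same base as the binding-domain percentages beside it in the text.

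In a tiered scheme the screening step passes some samples that the confirmatory step then rejects. Those samples would enlarge the denominator without being ADA-positive by the SAP's own definition, and the neutralizing rate would look lower than it is among subjects or samples with confirmed antibodies. What is at stake is the readability of one descriptive safety figure.

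**Working it through.** The documents give no neutralizing rate, assay count or confirmation rate. There is no planned figure to reproduce, so the check is algebra on the denominator plus a range of assumed values.

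**Notation**

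- S = number positive on the screening test (denominator in SAP 6.9)
- C = number positive on the confirmatory assay (definition of ADA-positive in SAP 6.9)
- T = number tested in the neutralizing assay (optional under protocol 8.7)
- N = number neutralizing

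**Reading used.** Confirmed positives are a subset of screening positives, and neutralizing testing is done on confirmed positives, so N ≤ T ≤ C ≤ S. The SAP does not spell this out. It is the natural reading of the first two sentences of 6.9, but the neutralizing sentence itself speaks only of samples that are further tested.

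**Formula.** The SAP percentage is

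N/S = (N/C) × (C/S).

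It cannot exceed N/C, and it equals N/C only when C = S (or N = 0). The relative understatement against confirmed positives is 1 − C/S, whatever the neutralizing rate.

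**Values.** All confirmed positives are assumed tested (T = C), and C/S is assumed over a range:

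| C/S (assumed) | Relative understatement | N/S when N/C = 50% | N/S when N/C = 20% |
|---|---|---|---|
| 1.00 | 0% | 50.0% | 20.0% |
| 0.90 | 10% | 45.0% | 18.0% |
| 0.75 | 25% | 37.5% | 15.0% |
| 0.50 | 50% | 25.0% | 10.0% |

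**Optional testing.** If some confirmed positives are never tested, they sit in the denominator and cannot enter the numerator. Take C = 60, C/S = 0.75, T/C = 0.8, and half of the tested samples neutralizing (all assumed). Then S = 60/0.75 = 80, T = 0.8 × 60 = 48 and N = 0.5 × 48 = 24, which gives

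- N/S = 24/80 = 30.0%
- N/C = 24/60 = 40.0%
- N/T = 24/48 = 50.0%

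Moving from S to C therefore removes the mismatch with the ADA definition but leaves the effect of untested samples. That effect is visible only if T is reported.

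**The case against.** The strongest reply is that the word 'screening' may simply be a slip. Everything else in SAP 6.9 runs on the confirmatory assay, and no screening assay for ADA is described in protocol 8.7, SAP 2.8 or SAP 6.9. If the confirmatory test was meant, there is no dilution and only a word to correct. The same holds if every screening positive confirms. This stands: the documents show an inconsistent and undefined denominator, not a demonstrated bias.

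A reader might go further and infer three things that the documents do not support.

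- *That the plan will certainly understate the neutralizing rate.* This needs a tiered assay with some screening positives failing to confirm, and the documents state neither.
- *That the percentage will disagree with ADA counts printed in the same table.* No ADA table layout is in the documents. SAP 6.1 leaves table formats, and exceptions to its default denominator, to separate shells.
- *That a secondary endpoint is compromised.* The secondary objective concerns the presence of ADAs, with treatment-emergent ADAs as the endpoint. Neutralizing activity is not a named endpoint, and its testing is optional.

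It can also be said that little is lost, because the neutralizing count is reported next to its percentage and confirmed positives are counted by visit. A reader could approximate the rate among confirmed positives. This stands in part: the numerator is sound, but 6.9 moves between subjects and samples, so the two counts need not be in the same unit.

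Finally, a denominator of tested samples only is not clearly better. Testing is optional and no selection rule is given, so N/T could overstate the rate if samples are not chosen at random. That also stands, and it shapes the fix.

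**Conclusion.** The point holds as an inconsistency inside SAP 6.9: the neutralizing percentage uses a test that the section does not define, while ADA status and the by-visit and binding-domain results use the confirmatory assay. Nothing in protocol 8.7, protocol 9.3.5, SAP 2.8 or SAP 4.5 resolves it.

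Its size cannot be computed from the documents. On the literal, tiered reading, the relative understatement is one minus the confirmation fraction, or 0% to 50% over the assumed range of 1.00 to 0.50. It is zero if all screening positives confirm or if the wording was a slip. Even then the sentence needs correcting, because it would be programmed as it stands.

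The consequence is limited to a descriptive summary of an optional assay. No efficacy endpoint, hypothesis test, power figure or sample size is involved. Lowest severity.

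**What to change.** In the neutralizing-antibody sentence of SAP 6.9:

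1. Change the denominator from positive on the screening test to positive on the confirmatory test.
2. Report beside it the number of confirmed positives actually tested for neutralization, so that the rate among tested can also be read and untested positives are not silently counted as non-neutralizing.
3. State whether the unit is samples or subjects, and use the same unit for numerator and denominator.
4. Add the percentage of the ADA Analysis Set (SAP 4.5). This figure should be in subjects.

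If a screening-positive denominator really is intended, the section should instead describe the screening test and report its positive count.

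The cost is one amended sentence with a short addition, and a check that the table shells agree. No further samples, assays or data collection are needed.

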## 7. Appendices

### Appendix 1: Document History

Document Version, Status, Date	Summary/Reason for Changes
Version 1.0, Final, 21JUN2023	Not applicable; First final version

### Appendix 2: End Points Definitions and Scoring Method

#### Appendix 2.1 Health Assessment Questionnaire Disability Index (HAQ-DI)

- The Disability Index

The eight categories assessed by the Disability Index are 1) dressing and grooming (2 items), 2) arising (2 items), 3) eating (3 items), 4) walking (2 items), 5) hygiene (3 items), 6) reach (2 items), 7) grip (3 items), and 8) activities (3 items).

- Scoring Conventions for the Disability Index

There are four possible responses for the Disability Index questions:

WITHOUT ANY DIFFICULTY = 0

WITH SOME DIFFICULTY = 1

WITH MUCH DIFFICULTY = 2

UNABLE TO DO = 3

The highest score for questions in each category (range 0 to 3) determines the score for the category. If either AIDS OR DEVICES and/or HELP FROM ANOTHER PERSON are checked for a category, the score is set to “2”, unless the score is already “3” (i.e., scores of “0” or “1” are increased to “2”). For example, if the highest score for the dressing category is “1”, and the patient says they use a device for dressing, the computed category score would be “2”. The sum of the computed categories scores is then calculated and divided by the number of categories answered. This gives a score in the 0 to 3 range. A disability index cannot be computed if the patient does not have scores for at least six (6) categories

The following list details how each aid and device is associated with the category scores:

HAQ-DI Category	AIDS OR DEVICES	HELP FROM ANOTHER PERSON
Dressing & grooming	Devices used for Dressing (button hook, zipper pull, etc.)	Dressing and grooming

Arising	Special or built up chair	Arising
Eating	Built up or special utensils	Eating
Walking	Crutches, Cane, Wheelchair, Walker	Walking
Hygiene	Raised toilet seat, Bathtub bar, Bathtub seat, Long-handled appliances in bathroom	Hygiene
Reach	Long-handled appliances for reach	Reach
Grip	Jar opener (for jars previously opened)	Gripping and opening things
Activities		Errands and chores

**Appendix 2.2 36-Item Short Form Survey (SF-36)**

The SF-36 questionnaire consists of eight scales yielding two summary measures: physical and mental health. The physical health measure includes four scales of physical functioning (10 items, PF), role limitations due to physical health (4 items, RP), bodily pain (2 items, BP), and general health (5 items, GH). The mental health measure is composed of vitality (4 items, VT), social functioning (2 items, SF), role limitations due to emotional problems (3 items, RE), and mental health (5 items, MH).

Two versions of the SF-36 were used in this study. SF-36v1 and SF-36v2®. A small subset of subjects received v1. For these subjects, coding will be done programmatically as follows.

- Step 1: Recoding Items

Item numbers	Change original response category *	To recoded value of:
1, 2, 20, 22, 34, 36	1	100
	2	75
	3	50
	4	25
	5	0
3, 4, 5, 6, 7, 8, 9, 10, 11, 12	1	0
	2	50
	3	100
13, 14, 15, 16, 17, 18, 19	1	0
	2	100
21, 23, 26, 27, 30	1	100
	2	80
	3	60
	4	40

	5	20
	6	0
24, 25, 28, 29, 31	1	0
	2	20
	3	40
	4	60
	5	80
	6	100
32, 33, 35	1	0
	2	25
	3	50
	4	75
	5	100

\* Precoded response choices as printed in the questionnaire.

- Step 2: Averaging Items to Form Scales

Scale	Number of items	After recoding per Step 1, average the following item
Physical functioning	10	3 4 5 6 7 8 9 10 11 12
Role limitations due to physical health	4	13 14 15 16
Role limitations due to emotional problems	3	17 18 19
Energy/fatigue/vitality	4	23 27 29 31

Emotional well-being/mental health	5	24 25 26 28 30
Social functioning	2	20 32
Bodily pain	2	21 22
General health	5	1 33 34 35 36

The SF-36 questionnaire consists of eight scales yielding two summary measures: physical and mental health. The physical health measure includes four scales of physical functioning (10 items, PF), role limitations due to physical health (4 items, RP), bodily pain (2 items, BP), and general health (5 items, GH). The mental health measure is composed of vitality (4 items, VT), social functioning (2 items, SF), role limitations due to emotional problems (3 items, RE), and mental health (5 items, MH).

From the individual subscales, two component summary scores are generated for physical (PCS) and mental health (MCS). The mean of the first five subscales (PF, RP, BP, GH, and VT) produce the PCS and the mean of the last five subscales (GH, VT, SF, RE, MH) produce the MCS; the GH and VT subscales overlap between the two overall components.

Items that are left blank (missing data) are not taken into account when calculating the scale scores. Hence, scale scores represent the average for all items in the scale that the respondent answered.

Scoring of the SF-36v.2 will be done using Quality Metrics.

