8.1.2.8. Short Form-36

The acute Short Form-36v2 Health Survey (SF-36) is 36-item questionnaire that measures 8 dimensions related to functioning and well being including physical functioning, role-function, bodily pain, general health, vitality, social functioning, role-emotional, and mental health.

The SF-36 questionnaire will be presented in local language and is to be completed by the subject at the designated study visits listed in the SoA ([Section 1.3](#)).

The subject should complete the questionnaire before site personnel perform any clinic assessments and before any interaction with the site personnel has occurred to avoid biasing the subject's response.

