**Appendix 2.6 Psoriatic Arthritis Disease Activity Score (PASDAS)**

The PASDAS is calculated using the following formula:

$$\text{PASDAS} = (0.18\sqrt{\text{IGADA}}) + (0.159\sqrt{\text{SGADA}}) - (0.253\sqrt{\text{SF-36PCS}}) + (0.101 * \ln(\text{SJC66}+1)) + (0.048 * \ln(\text{TJC68}+1)) + (0.23 * \ln(\text{LEI}+1)) + (0.37 * \ln(\text{LDI}+1)) + (0.102 * \ln((\text{CRP} * 10) + 1) + 2) * 1.5$$

where swollen and tender joint counts can range from 0 to 66 and 68 joints, respectively; and CRP = C-reactive protein measured in mg/L. The PASDAS score ranges from 0-10 with higher scores indicating worse disease activity.

where TJC=tender joint count and SJC=swollen joint count;

ln = natural logarithm; all VAS scores are from 0-100mm;

IGADA = investigator's global assessment of disease activity;

SGADA = subject's global assessment of disease activity;

PCS = physical component summary scale of the SF-36;

LEI = Leeds enthesitis index;

LDI = Leeds dactylitis index;

CRP = C-reactive protein measured in mg/dL.

The score range of the PASDAS is 0 to 10, with worse disease activity represented by higher scores.

**Appendix 2.7 Psoriatic Arthritis Impact of Disease Scoring and Calculation Rules  
(PsAID)**

The PsAID is calculated based on 9 Numerical rating scales (NRS) questions. Each NRS is assessed as a number between 0 and 10.

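### SF-36 v1 and v2 follow separate scoring routes with no stated common metric, yet PCS, MCS and PASDAS are each analysed as one variable

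*SAP*

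**What the plan says.** Protocol section 8.1.2.8 plans one instrument: "The acute Short Form-36v2 Health Survey (SF-36) is 36-item questionnaire".

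SAP Appendix 2.2 describes something different: "Two versions of the SF-36 were used in this study". It continues: "A small subset of subjects received v1. For these subjects, coding will be done programmatically as follows". Step 1 maps every item response to a value between 0 and 100. Step 2 forms the eight subscales: "After recoding per Step 1, average the following item". After a general description of the questionnaire comes the rule for the physical summary: "The mean of the first five subscales (PF, RP, BP, GH, and VT) produce the PCS". MCS is built the same way, with social functioning, role-emotional and mental health in place of the three physical subscales. General health and vitality count in both.

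For v2 the appendix has one sentence: "Scoring of the SF-36v.2 will be done using Quality Metrics". It does not say on what metric the v2 subscales, PCS or MCS are returned.

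SAP section 6.6.5 lists change from baseline in SF-36 total score, PCS and MCS, and change in PASDAS, each as one endpoint. At Week 16 they use the repeated-measures model of section 6.6.3, which has no term for questionnaire version. SAP Appendix 2.6 puts PCS into PASDAS through the term -0.253 × √PCS and defines it only as "PCS = physical component summary scale of the SF-36", naming neither version nor scale.

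**The concern.** A programmer working from this SAP cannot tell whether a v1 PCS and a v2 PCS are in the same units. If they are not, three things follow.

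- A given improvement counts for more in one subset than in the other when mean changes are compared.
- The pooled variance mixes two spreads.
- Two subjects in the same state of health can receive different PASDAS values because they filled in different forms.

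The SAP treats a comparable administration problem more carefully. Where the visual analogue scales were not given as intended, section 6.6.1 sets a rescaling rule and section 6.6.2 adds three supplemental analyses. The SF-36 version problem gets neither.

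**Working it through.** The plan states no figure that depends on this point, so there is nothing to reproduce. The check has four parts.

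**1. Range of a v1 score under the SAP rule.** The Step 1 table covers all 36 items. Setting every item to its worst and then its best recoded value gives PCS and MCS of 0 and 100, so both run from 0 to 100. Role-physical has four two-level items (0 or 100), and PCS averages five subscales. One such item therefore moves PCS by 100 / 4 / 5 = 5 points.

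**2. Range of a v2 score.** Neither document gives it. Whether v2 matches the 0-100 scale cannot be settled from the text.

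**3. Effect of mixed units on a mean difference.** Let *f* be the share of subjects on v1 and *k* the number of v1 units that equal one v2 unit. Assume the same share in each arm, the same underlying effect in both subsets, and one version per subject throughout.

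- Multiplier on the mean difference: (1 - *f*) + *f* × *k*
- Multiplier on the within-version variance: (1 - *f*) + *f* × *k*²

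The SAP says only that the v1 subset was small, and it gives no *k*. The ranges *f* = 2-10% and *k* = 1 to 2.5 are assumptions.

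| *f* | *k* | Mean difference × | Variance × |
|---|---|---|---|
| 2-10% | 1 | 1.00 | 1.00 |
| 2% | 2.5 | 0.98 + 0.05 = 1.03 | 0.98 + 0.125 = 1.105 |
| 5% | 2 | 0.95 + 0.10 = 1.05 | 0.95 + 0.20 = 1.15 |
| 10% | 2.5 | 0.90 + 0.25 = 1.15 | 0.90 + 0.625 = 1.525 |

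At the last row, the difference relative to its standard deviation becomes 1.15 / √1.525 = 0.93 of its single-scale value. The reported difference looks larger, while the comparison is slightly less precise.

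**4. Effect on PASDAS.** Over PCS 0-100 the term 0.253 × √PCS runs from 0 to 2.53. Suppose the same patient scores 40 on one scale and a higher value on the other (the offsets are assumed):

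| PCS pair | Shift in PASDAS |
|---|---|
| 40 and 45 | 0.253 × (√45 - √40) = 0.10 |
| 40 and 50 | 0.253 × (√50 - √40) = 0.19 |
| 40 and 60 | 0.253 × (√60 - √40) = 0.36 |

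These follow the brackets as printed in Appendix 2.6, where the factor 1.5 applies only to the last group (the CRP term plus 2). If the factor were meant for the whole sum, the shifts would be 0.15, 0.28 and 0.54. The stated PASDAS range is 0 to 10.

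**The case against.** The best defence is that a difference in units has not been shown. The rule for PCS and MCS follows a general description of the questionnaire and can be read as covering both versions. The appendix heading and the v2 sentence also cite the same scoring reference. On that reading the scales may coincide and nothing is lost. This stands as far as it goes: the size of the problem cannot be established from the documents. It does not close the gap, because v2 still goes through vendor scoring on an unstated metric.

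It is also true that the SAP never says in words that the versions are pooled. That is inferred from single analyses with no handling by version, but nothing in the plan points the other way.

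The endpoints are exploratory, with p-values declared descriptive. ACR50 and the six secondary endpoints do not use the SF-36. This limits the weight of the point and is accepted.

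Two stronger readings are tempting and should not be made.

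- **PASDAS turns negative on a 0-100 PCS.** With the factor 1.5 on the whole sum, a subject with no disease would score (2 - 2.53) × 1.5 = -0.80 at PCS 100 and fall below zero above PCS 62.5. A reader might take this as proof that the formula expects another scale. The printed brackets do not give that result: the same subject scores 2 × 1.5 - 2.53 = +0.47.
- **Subjects who changed version show a spurious change.** The SAP assigns version by subject and records no switching. If each subject kept one version, change from baseline stays within one scale, and only the comparison between subjects is affected.

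**Conclusion.** The point holds as a gap in specification. The plan sets two scoring routes, leaves one on an unstated metric, and analyses the results as one variable. Following it as written can mix units in SF-36 PCS, MCS and PASDAS.

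The consequence runs from none, if the scales coincide, to a mean difference multiplied by 1.15 and a within-version variance multiplied by 1.53 at the extreme of the assumed ranges. The v1 share, the unit ratio and the PASDAS offsets are all assumptions. A reader might infer that v1 changes necessarily carry two or more times the weight of v2 changes. The documents give no standard deviations for either version, and a ratio of 1 remains possible. No confirmatory conclusion is at risk. This is a cheap improvement.

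**What to change.** - State the output metric of the v2 scoring. Score v1 and v2 with the same algorithm on that one metric, and name it in Appendix 2.6 as the PCS that enters PASDAS.
- If v1 cannot be put on that metric, base the main SF-36 and PASDAS summaries on v2 only and list the v1 results separately. Alternatively, keep v1 in the main summaries and add a v2-only sensitivity analysis for both.
- Report the number of v1 subjects by arm and visit, and any change of version within a subject.
- While editing, define the SF-36 total score, which is analysed but has no formula in Appendix 2.2, and confirm the placement of the factor 1.5 in Appendix 2.6.

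The cost is SAP wording and a little programming. Under the v2-only option, a few v1 records also drop out of the main exploratory summaries. Retaining v1 with a sensitivity analysis avoids that loss but leaves the main figures on possibly mixed units.
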